## **Evaluation of Kinesiophobia and Physical Activity Levels in Patients with Fibromyalgia Syndrome and Chronic Neck Pain**

### **ABSTRACT**

**Introduction:** Kinesiophobia which is described as fear of movement reduces physical activity levels and increases the risk of chronic pain. Kinesiophobia has not been studied in detail in patients with fibromyalgia syndrome and chronic neck pain.

**Objective:** To evaluate pain, kinesiophobia, physical activity, depression, disease severity, and fatigue in patients with fibromyalgia syndrome or chronic neck pain and healthy controls.

**Design:** Cross-sectional study. Setting: Tertiary Health Care Center, Aksaray, Turkey  
Participants: 30 patients with fibromyalgia syndrome (Group 1), 30 patients with chronic neck pain (Group 2), and 30 healthy individuals (Group 3) were included.

**Main Outcome Measures:** Outcome measures were Visual Analogue Scale (VAS)-pain and fatigue, Tampa Scale of Kinesiophobia (TSK), Beck Depression Inventory (BDI), International Physical Activity Questionnaire (IPAQ) Short Form, Fibromyalgia Impact Questionnaire (FIQ), Neck Pain Disability Index (NPDI).

## INTRODUCTION

Fibromyalgia syndrome (FS) is a condition that generally affects young adult women aged 20 to 55 years, with a prevalence of 2-3% in the general population and unknown etiology. In addition to the widespread pain in the body, FS has a wide range of other symptoms, including sleep disorder, fatigue, depression, anxiety, cognitive impairment, headache, and gastrointestinal complaints (1). Almost all patients with FS complain of fatigue and report difficulty even performing daily tasks due to this complaint (2). Although exercise has an important role in the treatment of FS, the level of physical activity is reported to be lower in patients with FS than in healthy controls. It is considered that physical inactivity is caused by several factors, including fatigue, pain, and kinesiophobia. In addition to fatigue, FS patients with low levels of physical activity have been shown to have reduced pain threshold and pain inhibition, depression, pain catastrophizing, and fear of movement (3, 4). Described as fear of movement, kinesiophobia refers to avoidance of physical activity due to excessive fear and anxiety concerning pain, which reduces mobility and muscle strength and triggers more fear of movement, and this vicious circle increases the risk of chronic pain (5). In a study evaluating the fear of movement in FS cases, patients with a high level of fear and anxiety were found to have more insomnia, catastrophic thoughts, disability, negative emotions, depression, high pain intensity, lower physical performance, reduced cognitive performance, and a lower quality of life (6, 7). Thirty to fifty percent of the general population experience neck pain, one of the most common musculoskeletal complaints, in their lifetime. Neck pain is a common symptom among office workers, of whom 50% associated this pain with their occupation and 14% stated that it restricted their daily life activities (8, 9). In general, it has been shown that the frequency and severity of neck pain are reduced in office workers who exercise or engage in sportive activities and that the risk of chronic pain increases in those that are physically inactive (10, 11). In patients with neck pain, fear of movement caused by fear avoidance beliefs and behaviors results in restriction of physical activity and development of chronic pain, leading to depression, disability, and reduced job performance and quality of life (12, 13). In this study, we evaluated pain, kinesiophobia, physical activity, depression, disease severity, and fatigue in patients with FS and chronic neck pain (CNP), and healthy controls. We aimed to identify the factors related to kinesiophobia and restricted physical activity to take the necessary measures to prevent these behaviors.

## METHODS

### Study Design

We assessed pain intensity, kinesiophobia, fatigue, depression, physical activity level and disability in patients with FS and CNP, and healthy individuals in this cross-sectional study. The patients were recruited from a physical medicine and rehabilitation outpatients clinic of Aksaray University Training and Research Hospital, Aksaray, Turkey. The healthy control group was consisting of doctors, nurses, medical secretaries who work in Aksaray University Training and Research Hospital, and patient care providers that have no pain and additional diseases. Following the Helsinki Declaration, our study was approved by the Ethics Committee of Aksaray University Training and Research Hospital

(26.9.18, reference number: 2018/155) and written informed consent was obtained from all the participants.

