## **Participants**

Thirty patients with a diagnosis of FS according to the 2016 revised ACR FS diagnostic criteria and a disease duration of longer than three months; 30 patients with CNP lasting for more than three months, and 30 healthy controls without pain or additional disease were included in the study that was conducted between October 2018 and December 2018. All the participants were aged 18 to 65 years. The exclusion criteria were malignancy, systemic infectious and rheumatic diseases, history of operation, having received physical therapy or intra-articular or intra-ligamentary injection within the last three months, previous diagnosis of a psychological or cognitive disorder, and history of pregnancy.

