## **Main Outcome Measures**

The demographic data of the participants were recorded on a personal information form. Pain intensity and fatigue were evaluated by the Visual Analogue Scale (VAS), kinesiophobia by the Tampa Scale of Kinesiophobia (TSK), depression by the Beck Depression Inventory (BDI), physical activity level by the International Physical Activity Questionnaire (IPAQ) Short Form, functional status in patients with FS by the Fibromyalgia Impact Questionnaire (FIQ), and neck pain-related disability in the neck pain group by the Neck Pain Disability Index (NPDI). The details of the implementation of the instruments are as follows: Visual Analog Scale (VAS) for the Evaluation of Pain and Fatigue For this evaluation, the patient is asked to mark his/her severity of pain and fatigue on a horizontal 10-cm line with number 0 on one end representing “no pain or no fatigue” and number 10 on the other end indicating “very severe pain or very severe fatigue” (14, 15). Tampa Scale of Kinesiophobia (TSK) Based on a four-point Likert type, this scale contains 17 items that evaluate fear and anxiety related to physical activity. A total score of greater than 37 is accepted as statistically significant and interpreted as a high level of kinesiophobia. The validity and reliability analysis of the Turkish version of TSK was undertaken by Yilmaz et al. (16). Beck Depression Inventory (BDI) This is a 21-item questionnaire that investigates the characteristic attitudes and symptoms of depression. A score of 10 or higher indicates depression (17). International Physical Activity Questionnaire (IPAQ) Short Form IPAQ consists of seven items that measure the duration of the participants’ physical activity, walking and sitting within the last seven days in the MET-min/week unit (18). Fibromyalgia Impact Questionnaire (FIQ) FIQ aims to evaluate the arthritis symptoms and functional status of patients with FS through 21 questions that inquire about physical functions, work-related situations, depression, anxiety, waking up tired, pain, stiffness, and fatigue. The validity and reliability of the Turkish version of FIQ was tested by Ediz et al. (19). Neck Pain Disability Index (NPDI) This index consists of 20 questions that assess severity of neck pain and the extent to which the pain affects the social, professional and daily activities of patients (20).

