## **Statistical Analysis**

Statistical analysis was performed using the Statistical Package for the Social Sciences (SPSS) v. 15.0. Descriptive statistics were given as mean  $\pm$  standard deviation (SD) for

variables with normal distribution, and frequency tables for ordinal and categorical variables. We chose to conduct the Kolmogorov-Smirnov test for the normalization analysis. The MannWhitney U test was employed for paired comparisons of numerical sociodemographic data, chi-square test for the paired comparison of categorical sociodemographic data and the comparison of sociodemographic data (except age and disease duration) between three groups, and one-way analysis of variance (ANOVA) for the comparison of age and disease duration between the three groups. Before conducting one-way ANOVA, the Levene test was performed to test the homogeneity of variance. Since the result of this test was  $p > 0.05$  for VAS-fatigue, TSK and BDI, the Tukey test was employed for post hoc analysis. For VASpain and FIQ that produced  $p < 0.05$  in the Levene test, the Games-Howell post hoc test was preferred. Spearman's correlation analysis was undertaken individually for each group. The level of statistical significance was accepted as  $p < 0.05$

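### Control contrasts on TSK, BDI and VAS-fatigue set clinic patients against pain-free hospital staff and care providers, with no age or sex matching and no adjustment

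*Combined protocol and SAP*

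**What the plan says.** The Study Design section gives different sources for patients and controls. For FS and CNP: "The patients were recruited from a physical medicine and rehabilitation outpatients clinic". The controls are "doctors, nurses, medical secretaries who work in Aksaray University Training and Research Hospital, and patient care providers that have no pain and additional diseases". Nothing there or under Participants describes individual matching, frequency matching or stratified selection. The one limit on age common to all groups is: "All the participants were aged 18 to 65 years".

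On covariates, Main Outcome Measures says: "The demographic data of the participants were recorded on a personal information form". The fields of that form are not listed.

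Statistical Analysis provides demographic comparisons of two kinds. Across three groups it uses one-way ANOVA "for the comparison of age and disease duration between the three groups" and chi-square for the other sociodemographic data. In pairs, the Mann-Whitney "U test was employed for paired comparisons of numerical sociodemographic data, chi-square test for the paired comparison of categorical sociodemographic data". It does not say which pairs are tested or what follows if a difference is found.

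For the outcomes it says: "Before conducting one-way ANOVA, the Levene test was performed to test the homogeneity of variance", and "for VAS-fatigue, TSK and BDI, the Tukey test was employed for post hoc analysis". That TSK, BDI and VAS-fatigue were compared by one-way ANOVA is inferred from these two statements. No ANCOVA, regression or stratified analysis is mentioned.

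**The concern.** The groups are not randomised, so nothing in the design makes their age and sex distributions alike. The Introduction describes FS as mainly a condition of women between 20 and 55, which gives the FS group a particular profile. Controls drawn from staff and care providers need not share it within an age range of 47 years.

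If the controls do differ in age or sex, and these relate to fear of movement, depression score or fatigue, part of the observed difference would be credited to FS or CNP. The demographic tests do not prevent this. A moderate gap can escape them at 30 per group. A large gap would usually be seen, but the plan as written still reports the unadjusted comparison.

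The concern is confined to contrasts with the controls. How the controls were chosen does not affect FS versus CNP or the Spearman correlations within the patient groups.

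**Working it through.** The documents give no sample-size calculation, SD, effect size, or age or sex distribution, so there is no stated figure to reproduce. What follows shows a range under assumptions.

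**From the documents:** 30 per group (Abstract, Participants); significance level 0.05 (Statistical Analysis); three groups, hence 2 and 87 degrees of freedom for the omnibus F test.

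**Assumed:** age SD 11 years; outcome changes by 0.02 to 0.04 SD per year; sex effect 0.3 to 0.5 SD; 90% women in both patient groups; no disease effect; only the controls differ.

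**Bias in a control contrast:** b = (age gap × slope) + (difference in proportion of women × sex effect). For example, 5 × 0.02 = 0.10 and 5 × 0.04 = 0.20; for 90% v 70% women, 0.2 × 0.3 = 0.06 and 0.2 × 0.5 = 0.10.

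**Omnibus false-positive rate:** non-central F(2, 87) with λ = 30 × Σ(μ − mean)². For μ = (0, 0, b) this is 30 × (2/3)b² = 20b². So b = 0.20 gives λ = 0.8 and a rate of 11.3%; b = 0.40 gives λ = 3.2 and 33.0%.

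**Chance that the demographic tests flag the imbalance:** for age with the three-group ANOVA, the same F with b = 5/11 (λ = 4.13) gives 41.5%, and b = 10/11 (λ = 16.53) gives 95.6%. The chi-square rates and the any-test rates come from simulation. The any-test column assumes that the pairwise tests include both control pairs; with no imbalance it is 9.8% for age and 10.7% for sex.

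| Imbalance in controls | Bias (SD) | False-positive rate, unadjusted | Flagged: three-group test / any test |
|---|---|---|---|
| 5 years | 0.10 to 0.20 | 6.5 to 11.3% | 41.5% / 56.0% |
| 10 years | 0.20 to 0.40 | 11.3 to 33.0% | 95.6% / 98.0% |
| 90% v 70% women | 0.06 to 0.10 | 5.5 to 6.5% | 54.5% / 66.4% |
| 90% v 60% women | 0.09 to 0.15 | 6.2 to 8.4% | 84.9% / 90.2% |

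**Both imbalances, biases in the same direction** (simulation, 20,000 runs per setting; low effects, then high):

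| Setting | Bias (SD) | Unadjusted | Group + age + sex | Group + age |
|---|---|---|---|---|
| 5 years and 90% v 70% | 0.16, 0.30 | 8.8%, 20.2% | 5.0%, 4.8% | 5.5%, 6.6% |
| 10 years and 90% v 60% | 0.29, 0.55 | 18.4%, 56.2% | 4.9%, 5.1% | 5.9%, 8.8% |

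**Biases in opposite directions:** the bias falls to 0.10 − 0.06 = 0.04 or 0.20 − 0.10 = 0.10 in the first setting, and to 0.20 − 0.09 = 0.11 or 0.40 − 0.15 = 0.25 in the second. By the same F formula the rates are 5.2%, 6.5%, 6.8% and 15.1%.

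**If the model is imperfect:** with a quadratic age effect of 0.1 SD per squared age-SD left out, the model with group, age and sex still gives 4.9 to 5.2% in the combined settings, with residual bias of at most 0.03 SD.

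**The case against.** The strongest reply is that no imbalance has been shown. Every gap and effect size above is assumed, and with balanced groups the bias is zero. That stands, and it is why the point is worded as possible confounding.

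Second, the plan does look at demographics, and on the figures above a single imbalance large enough to matter would usually be noticed. That also stands in part. But noticing is not adjusting, and no action is attached to the tests.

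Third, the large combined figures assume that age and sex push the outcome the same way. The documents do not say which direction applies. If the two oppose, the rates drop to about 5 to 15%, so the combined table is an upper case.

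Fourth, age and sex are only part of what separates staff and care providers from clinic patients. Occupation, and selection for having no pain and no other disease, remain after adjustment. This is correct: the near-nominal rates for the adjusted model hold only if age and sex are the sole confounders.

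Fifth, the study ran from October to December 2018, so matching is no longer possible, and sex is not named among the variables. Also, a large true disease difference would survive a bias of 0.06 to 0.30 SD as a conclusion, though not as an estimate. These replies limit the remedy to a reanalysis and a stated limitation; they do not remove the reason for it.

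**Conclusion.** The concern holds. Controls come from a different source than patients, no matching is described, and the outcome comparisons are unadjusted. The demographic tests are balance checks without consequence. Whether confounding occurred, and in which direction, cannot be told from the documents.

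Under the stated assumptions, a single imbalance likely to go unseen has a small effect: at most 0.2 SD, with an omnibus error rate of at most 11.3%. A large or combined imbalance can do much more (up to 0.55 SD and 56.2% in the worst case examined), but would usually be visible and still not adjusted for. Because adjustment is cheap and the size is unknown, this should be corrected. It does not by itself invalidate the study.

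**What to change.** Report the three-group comparisons of TSK, BDI and VAS-fatigue from a linear model with group, age and sex, regardless of the demographic test results. Give adjusted mean differences with 95% confidence intervals and multiplicity-adjusted contrasts, beside the unadjusted results. Label this a reanalysis, since Statistical Analysis already reports the Levene results. Use the same model for any IPAQ comparison, transformed if skewed.

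Age is named in Statistical Analysis. Take sex from the personal information form; if it was not recorded, adjust for age alone and say so, accepting that this leaves up to 8.8% in the worst case above.

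Word the control contrasts as being against pain-free hospital staff and patient care providers, and state that occupational and healthy-control selection is not removed.

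**Cost.** Two of 87 residual degrees of freedom: the critical t moves from 1.9876 to 1.9883. The standard error of a control contrast is multiplied by √[(2/30 + gap²/(87 × 121) + d²/(87v)) / (2/30)], where d is the difference in proportion of women and v = (0.09 + 0.09 + p(1 − p))/3, with p the proportion of women among controls. This gives increases of:

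- 1.8% for 5 years and 6.9% for 10 years;
- 2.6% for 90% v 70% women and 5.4% for 90% v 60%;
- 4.3% and 12.0% for the two combined settings (5.7% and 13.4% in simulation, which adds chance imbalance).

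Against that, age would reduce the residual SD by 2% to 10% under the assumed slopes: √(1 − 0.22²) = 0.976 and √(1 − 0.44²) = 0.898, where 0.22 and 0.44 are 11 years times the slope. No new participants are needed, only slightly more analysis work.

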## **Participants**

Thirty patients with a diagnosis of FS according to the 2016 revised ACR FS diagnostic criteria and a disease duration of longer than three months; 30 patients with CNP lasting for more than three months, and 30 healthy controls without pain or additional disease were included in the study that was conducted between October 2018 and December 2018. All the participants were aged 18 to 65 years. The exclusion criteria were malignancy, systemic infectious and rheumatic diseases, history of operation, having received physical therapy or intra-articular or intra-ligamentary injection within the last three months, previous diagnosis of a psychological or cognitive disorder, and history of pregnancy.

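### Controls must be free of any other disease but patients need not be, so unlisted comorbidity cannot be separated from FS or CNP in the patient-control contrasts

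*Combined protocol and SAP*

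**What the plan says.** **Controls.** The Participants section says that "30 healthy controls without pain or additional disease were included in the study". Study Design repeats the condition: the control group is made up of hospital doctors, nurses and medical secretaries, and "patient care providers that have no pain and additional diseases".

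**Patients.** The FS group is "Thirty patients with a diagnosis of FS according to the 2016 revised ACR FS diagnostic criteria and a disease duration of longer than three months". The CNP group is "30 patients with CNP lasting for more than three months". Neither description requires freedom from other disease.

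**Exclusions.** "The exclusion criteria were malignancy, systemic infectious and rheumatic diseases, history of operation" opens the list. It goes on to physical therapy or certain injections in the preceding three months, and ends with "previous diagnosis of a psychological or cognitive disorder, and history of pregnancy". Ages run from 18 to 65.

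**Purpose and analysis.** The abstract gives the objective as "To evaluate pain, kinesiophobia, physical activity, depression, disease severity, and fatigue in patients with fibromyalgia syndrome or chronic neck pain and healthy controls". Statistical Analysis names one-way ANOVA, with Tukey post hoc tests for VAS-fatigue, TSK and BDI, and Spearman correlations within each group. It names no between-group test for IPAQ, and no covariate, matching or stratification. Main Outcome Measures mentions demographic data on a personal information form but no comorbidity item.

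**The concern.** Two groups that are compared with each other are held to different rules on disease other than the one under study. Followed as written, a person with FS and diabetes is eligible, while an otherwise suitable control with diabetes is not. Heart, lung or neurological disease gives the same result. Such diseases can plausibly raise fatigue and depression scores and reduce activity on their own.

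The asymmetry comes from the eligibility rule, so equal age and sex across groups would not remove it. Its expected direction is towards a larger patient-control difference. At stake is how a difference in fatigue, depression score or activity between patients and controls is interpreted: part of it may reflect general ill health rather than FS or CNP.

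**Working it through.** The documents contain no sample-size, effect-size or SD figure on this point, so there is no stated figure to reproduce. The check is a comparison of the rules, followed by an illustration of size.

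**1. The rules side by side**

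| | Controls | FS and CNP patients |
|---|---|---|
| Listed exclusions (not tied to one group) | apply | apply |
| Any other disease | not allowed | allowed |
| Comorbidity recorded | not mentioned | not mentioned |
| Comorbidity adjusted for | not mentioned | not mentioned |

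Only the second row differs between the columns, and nothing later in the plan compensates for it. The two patient groups share one column, so the rule does not create an FS-CNP difference. The Spearman analyses stay within a group and involve no patient-control contrast.

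**2. Inflation of the patient-control difference**

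Inflation = (prevalence in patients − prevalence in controls) × shift in SD units, with prevalence 0 in controls by rule. The documents give no values for the rest. Assumed: prevalence 20-40% in both patient groups, shift 0.3-0.8 SD.

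- Low: 0.20 × 0.3 = 0.06 SD
- Middle: 0.30 × 0.5 = 0.15 SD
- High: 0.40 × 0.8 = 0.32 SD

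**3. Effect on the planned test**

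Simulated: three groups of 30 (from the abstract), SD 1, no true effect of FS or CNP, each patient carrying the shift with the stated prevalence, and Tukey at 0.05. There were 200,000 runs per row.

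| Inflation | A given patient-control pair | Either patient-control pair | FS-CNP |
|---|---|---|---|
| 0 | 1.9% | 3.6% | 1.9% |
| 0.06 SD | 2.3% | 4.1% | 2.0% |
| 0.15 SD | 3.9% | 6.9% | 2.1% |
| 0.32 SD | 11.8% | 19.5% | 2.2% |

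An unadjusted two-sample t-test (58 df, noncentrality = inflation × √15) gives 5.6%, 8.8% and 23.0% for the last three rows. That is not the test the plan names, so the Tukey figures are the relevant ones.

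**4. Scale**

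With 30 per group, a simple two-group comparison has 80% power (two-sided 0.05, normal approximation) for (1.960 + 0.842) × √(2/30) = 0.72 SD. An inflation of 0.06 SD is negligible against that. One of 0.32 SD is a little under half of it (0.32 / 0.72 = 0.44).

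**The case against.** A healthy control group is meant to be healthy, and a disease-free reference is a legitimate choice. That stands, but it does not answer the point: the patients are not held to the same rule for diseases other than their own.

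The exclusion list also does more than a quick reading suggests. Taken literally, history of operation removes many people with serious past illness, and the exclusion of diagnosed psychological disorder narrows the route to a higher BDI. Both points stand in part. They reduce the room for bias but do not close it, because unlisted somatic disease remains allowed in patients.

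A reader might infer that the bias is known to be present. The documents do not support that: they give no comorbidity data, so they show an opportunity for bias and not its occurrence.

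A reader might also infer that the study claims the whole patient-control difference for FS or CNP. The abstract says only that the measures are evaluated in the three groups, and the introduction speaks of identifying factors related to kinesiophobia and restricted activity. The related-factors aim fits the within-group correlations, which this asymmetry does not bias.

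Finally, Statistical Analysis names no between-group test of IPAQ. For activity the point rests on the objective and not on a specified comparison.

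**Conclusion.** The point holds for the FS-control and CNP-control contrasts. In these, the effect of unlisted comorbidity on fatigue, depression score and activity cannot be separated from that of FS or CNP. It does not extend to the FS-CNP contrast or to the within-group correlations, and it does not show that any particular difference is spurious.

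The size is unknown. Under the assumed ranges, the error rate for at least one patient-control difference runs from about 4%, close to the 3.6% expected without inflation, to about 19%. For a given pair it runs from about 2% to 12%. The upper figures need both extreme assumptions together, and all of them assume equal comorbidity in the two patient groups and none in controls.

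**What to change.** In principle, apply one comorbidity rule to all three groups: either require the absence of other diseases in patients too, or allow the same conditions in controls. Participants were studied from October to December 2018, so the practical steps are these:

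1. Take comorbidity (yes/no) for each patient from the clinic record and report it by group.
2. Repeat the patient-control comparisons of VAS-fatigue, TSK and BDI in patients without additional disease. Add IPAQ if it is compared between groups. Present this beside the main analysis as a sensitivity analysis, not in its place.
3. If a difference does not persist there, or comorbidity cannot be retrieved, state the limitation and do not attribute the whole difference to FS or CNP.

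The cost is one data field, if the records hold it, and one further analysis. The downside is precision. If 20-40% of 30 patients drop out, 24 to 18 remain per patient group. The standard error factor rises from √(1/30 + 1/30) = 0.258 to √(1/24 + 1/30) = 0.274 or √(1/18 + 1/30) = 0.298, so intervals are about 6% to 15% wider. Loss of significance alone should therefore not be read as loss of the difference; compare the estimates and intervals. The restricted analysis also leaves other patient-control differences in place, such as the recruitment of controls from hospital staff.
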